**Study protocol, October 10th 2017**

**Cleansing efficacy of waist-shaped interdental brushes. A randomized-controlled crossover study.**

### *Rationale*

The use of interdental brushes is the most effective method to remove biofilm from interproximal sites. Oral line angles are predilection sites of plaque accumulation when interdental brushes are inserted buccally / labially only. The aim of this study is to compare the cleansing efficacy of waist-shaped interdental brushes (Circum®, Topcaredent, Zurich, CH) with that of cylindric interdental brushes (IDB, Topcaredent, Zurich, CH) in interproximal sites in periodontal maintenance patients.

The null hypothesis is that there will be no difference in plaque indices between the two interdental brushes at interproximal tooth sites of patients with opened interdental spaces.

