### *Study subjects*

Twenty periodontal patients of the University Hospital of Dental Prosthetics and Restorative Dentistry, Medical University of Innsbruck

Inclusion criteria:

- Completion of active periodontal treatment
- Maximum probing pocket depths of 5 mm
- No site  $\geq 4$  mm with bleeding on probing
- Bleeding on probing  $< 10\%$
- Open interproximal spaces both, in mandible and maxilla
- Presence of  $> 23$  natural teeth with no need for prosthetic rehabilitation

Exclusion criteria:

- Oral or systemic diseases other than periodontitis
- Mucosal / periodontal swelling or suppuration
- Pregnancy
- Minority
- Need for frequent drug consumption

Teeth with ceramic restorations and implants are excluded from analysis.

Recruitment period: September 1st to November 30th 2017

Data collection period: December 1st to March 30th 2018

*Clinical parameters*

Primary outcome measure: Plaque index by Quigley and Hein modified by Turesky et al. 1970 (T-QHI) (Turesky et al., 1970)

Secondary outcome measure: papillary bleeding index (PBI) by Saxon and Mühlemann (Saxon et al., 1977)

Both are assessed by two blinded and calibrated examiners at four sites per tooth: mesiobuccal, distobuccal, mesiolingual, and distolingual including the line angles.

*Clinical intervention*

Visit 1:

- 1) Pre-intervention: professional tooth cleaning.
- 2) Each proband is instructed by one dental hygienist with two sizes of waist-shaped test and cylindric control brushes, respectively, to guide the brushes from the buccal / labial side through the interdental spaces of all teeth four times each.
- 3) Randomization to group 1 or group 2 is performed by the toss of a coin.

First intervention period 30 days: Group 1 starts with using waist-shaped and group 2 starts with using cylindric brushes.

Visit 2:

- 1) Primary and secondary outcome parameters are measured (two calibrated blinded examiners)
- 2) Professional tooth cleaning
- 3) Re-instruction by the dental hygienist

Second intervention period 30 days: Group 2 using waist-shaped and group 1 using cylindric brushes.

Visit 3:

- 1) Primary and secondary outcome parameters are measured (two calibrated blinded examiners)
- 2) Professional tooth cleaning

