In addition, probands use the electric toothbrush (Oral-B® CrossAction, Procter & Gamble, Taunus, D) with toothpaste (Colgate total original®, Colgate & Palmolive, Vienna, AT) and are instructed not to use any chemical oral rinsing solution during the study period.

*Statistical analysis*

Sample size calculation is based on a study by Chongcharoen et al. 2012.

For descriptive analysis, median and interquartile range are given. The mode is defined as the T-QHI and PBI grade most often measured in an individual. On the site level, T-QHI is converted into a dichotomous index, and the odds ratio and confidence interval (CI) for establishing plaque free interdental sites are calculated with logistic regression analysis with a significance level of  $p < 0.05$ .

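### No oral-side brush estimate is pre-specified, although oral-side plaque motivates the trial and lingual sites are scored separately; the overall odds ratio does address the stated aim and null

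*Combined protocol and SAP*

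**What the plan says.** The Rationale gives one specific mechanism: "Oral line angles are predilection sites of plaque accumulation when interdental brushes are inserted buccally / labially only". The aim stated there is broader, a comparison of cleansing efficacy "in interproximal sites in periodontal maintenance patients", and the null is equally broad: "no difference in plaque indices between the two interdental brushes at interproximal tooth sites". Neither is split by side.

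Under Clinical intervention, each participant is instructed "to guide the brushes from the buccal / labial side through the interdental spaces of all teeth", which is the condition the Rationale describes. Under Clinical parameters, T-QHI and PBI are scored at "four sites per tooth: mesiobuccal, distobuccal, mesiolingual, and distolingual including the line angles", so each tooth contributes two buccal and two lingual scores.

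Under Statistical analysis, "On the site level, T-QHI is converted into a dichotomous index", and an odds ratio with CI "for establishing plaque free interdental sites are calculated with logistic regression analysis". The section lists no model terms of any kind. It names no aspect (lingual or buccal) term, stratum or interaction, no lingual summary, and no handling of sites clustered within patients or of the crossover periods.

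**The concern.** The plan names a mechanism on the oral side, recreates the insertion that should produce it, and collects side-specific scores. It does not say how the oral side will be reported.

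A single odds ratio over all sites mixes the two aspects. A positive result would not show that the oral side improved, and a null result would not show that it did not. If the lingual result is first looked at after the data are in, readers cannot tell it from one of several subgroups that might have been picked.

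A separate matter affects any site-level odds ratio here, pooled or lingual. If the logistic regression is fitted in its plain form, it treats the many sites in one mouth as independent.

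**Working it through.** **Inputs from the documents.** 20 patients; two-period crossover; more than 23 natural teeth, so at least 24; four sites per tooth. Before exclusions, that is at least 24 × 2 = 48 lingual and 48 buccal sites per patient and period. No plaque-free rate, effect size, variance or power is given. The sample size of 20 therefore cannot be reproduced, and every rate, odds ratio and SD below is an assumption.

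**1. One pooled odds ratio does not locate the effect.** Assume cylindric-brush plaque-free rates of 50% buccal and 30% oral. The pooled control rate is (0.50 + 0.30)/2 = 0.40, odds 0.667. A pooled OR of 1.5 gives odds 1.0, a test rate of 0.50. This arises from either of two cases:
- Oral effect only: oral rate 2 × 0.50 − 0.50 = 0.50, so OR = 1.0/0.4286 = 2.33.
- Buccal effect only: buccal rate 2 × 0.50 − 0.30 = 0.70, so OR = 2.333/1.0 = 2.33.

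Opposite effects nearly cancel. Oral OR 2.0 gives 0.462 and buccal OR 0.5 gives 0.333; the mean is 0.397 and the pooled OR is 0.99.

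**2. Pooling does not always cost power.** Assume control rates of 40% lingual and 60% buccal, and lingual OR 2.0 (rate 0.571). The pooled control rate is 0.50.

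| Buccal OR | Buccal test rate | Pooled test rate | Pooled OR | All-site power | Lingual-only power |
|---|---|---|---|---|---|
| 1.0 | 0.600 | 0.586 | 1.41 | 20–78% | 49–100% |
| 1.5 | 0.692 | 0.632 | 1.72 | 44–99% | 50–100% |
| 2.0 | 0.750 | 0.661 | 1.95 | 62–100% | 50–100% |

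Power is from simulation with paired t-tests on patient-level proportions. Assumed logit-scale SDs are patient 0.8, patient-period 0.3/0.5/0.7 and aspect-specific 0.1/0.3/0.5/0.7, which makes 12 settings. No figure in the documents favours one row. At buccal OR 1.0, a lingual test run only after a significant overall test has 19–78% power, so gating would lose most where the effect is oral only.

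**3. The lingual score is a proxy.** Suppose a site is plaque-free only if the line angle and the remaining surface both are, independently, with a 40% control rate for the site. Let only the line angle improve, with OR 2.0.
- Line angle 50% (remainder 80%): 0.667 × 0.80 = 0.533, site OR 1.71.
- Line angle 60% (remainder 66.7%): 0.75 × 0.667 = 0.50, site OR 1.50.
- Line angle 80% (remainder 50%): 0.889 × 0.50 = 0.444, site OR 1.20.

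With the same 12 settings, lingual-only power is about 8–25% at OR 1.2, 21–78% at 1.5 and 33–96% at 1.71, against about 51–99% at 2.0.

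**4. Clustering, for both odds ratios.** Plain logistic regression at 40% uses a log-OR variance of 2/(960 × 0.4 × 0.6) = 0.0087, where 960 = 20 × 48. The CI factor is exp(1.96 × √0.0087) = 1.20. It leaves out the patient-period and aspect-specific variation. On the patient-specific logit scale this adds 2 × (0.3² + 0.1²)/20 = 0.010 in the mildest setting and 2 × (0.7² + 0.7²)/20 = 0.098 in the strongest. Even the mildest addition exceeds the variance that is counted.

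In simulation with no brush effect, false positives at nominal 5% are about 14–48% for the lingual OR and 22–55% for the overall OR. A patient-clustered GEE with a Mancl–DeRouen variance and a t reference on 18 degrees of freedom gives about 4–5%. An uncorrected sandwich with a normal reference gives 7–10% for the lingual OR.

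**5. Precision to expect.** A patient-specific lingual OR of 2.0 corresponds to a population-averaged 1.69–1.82, with a median CI factor of 1.32–1.80. Typical intervals run from 1.82/1.32 to 1.82 × 1.32, that is 1.38–2.40, to 1.69/1.80 to 1.69 × 1.80, that is 0.94–3.04. At the proxy ORs of 1.2–1.7 the estimate sits closer to 1 and the interval will include 1 more often. Interaction power is 45–99% at buccal OR 1.0 and 12–42% at 1.5, again for lingual OR 2.0.

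**The case against.** The strongest reply is that nothing stated as an objective is missed. The oral line angle appears in one background sentence and not in the aim, the null or the outcomes, and the planned odds ratio matches the scope of both aim and null. This stands. A reader might infer that the trial analyses the wrong quantity, or that the lingual comparison should become primary; the documents do not support either.

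A reader might also infer that the plan rules out an oral-side answer. It does not. The analysis section lists no covariates at all, not even brush, so an aspect term is unspecified rather than excluded. The gap is one of pre-specification, and the data will exist.

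It is tempting to argue that pooling wastes power. All-site power ranges from 46 points below to 20 points above lingual-only power, depending on an unknown buccal effect, so this gives no general case. The power figures for a lingual OR of 2.0 are also optimistic if only the line angle changes.

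The clustering error should not be counted as evidence for the lingual gap. It affects the overall odds ratio at least as much and needs correcting whether or not a lingual estimate is added.

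Finally, a lingual estimate would not settle the line-angle question, because the scores cover the line angle together with the rest of the site. That limits the claim but does not remove the value of saying beforehand how the oral side will be reported.

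**Conclusion.** The concern holds in a limited form. The plan pre-specifies one odds ratio over interdental sites and no oral-side estimate, although oral-side plaque is its motivation and lingual scores are collected. The overall odds ratio answers the stated null. Unless an aspect term is added, it leaves open on which side any difference lies, and an oral-side result added later would be post hoc. This merits a secondary estimate and no change to the primary question.

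Separately, plain site-level logistic regression would understate uncertainty for both odds ratios. The documents do not say how clustering is handled, so this applies if the regression is fitted as literally described. The direction is secure for any appreciable patient-period variation. The sizes, about 14–48% and 22–55% false positives, depend on the assumed SDs.

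The pooled-OR and proxy results are exact arithmetic on assumed rates. With 20 patients and a proxy score, the lingual result is an estimate with a possibly wide CI, and a CI that includes 1 should not be read as showing no oral-side effect.

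**What to change.** Keep the overall brush effect as primary and PBI as the secondary outcome. Before analysis, add text to this effect under Statistical analysis:

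> The primary effect is the overall odds ratio (waist-shaped versus cylindric) for plaque-free status, from a logistic GEE with patients as clusters, a bias-corrected sandwich variance, a t reference distribution, and terms for brush, aspect, period and sequence. As secondary estimates, the brush odds ratio with 95% CI is reported for lingual (mesiolingual and distolingual) sites, and for buccal sites for comparison, whatever the overall result. These come from the same model with a brush-by-aspect interaction added. The interaction test is supportive only. The same dichotomised T-QHI is used throughout. The lingual score is a proxy for the oral line angle.

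The secondary estimates and the clustered model are separate changes. The second should be made even if the first is declined.

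Cost: no new data, since the four sites are already scored separately. It adds one secondary comparison and two model fits to specify and program, with and without the interaction. CIs will be wider than plain logistic regression would print: for the lingual OR, a factor of 1.32–1.80 against 1.20 under the assumed variances.

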### *Ethical approval*

The study was approved by the Ethics Committee of the Medical University of Innsbruck, Austria (ID AN5123).

### *Study design*

Randomized-controlled by toss of a coin

Single-blind: Two calibrated examiners

Crossover: Two intervention periods of 30 days each; wash out period one week

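### Coin-toss allocation of 20 crossover patients, with no period term named in the analysis, lets part of any period effect into the brush odds ratio

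*Combined protocol and SAP*

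**What the plan says.** Allocation is described twice. Study design has "Randomized-controlled by toss of a coin", and Visit 1 under Clinical intervention has "Randomization to group 1 or group 2 is performed by the toss of a coin". No block, target group size or balancing rule is given for the 20 patients. The sequences are then defined: "Group 1 starts with using waist-shaped and group 2 starts with using cylindric brushes", with the brushes exchanged for the second 30 days.

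Professional cleaning and hygienist instruction come before both periods. At Visit 1, "Each proband is instructed by one dental hygienist with two sizes of waist-shaped test and cylindric control brushes". At Visit 2, after the first measurement, there is cleaning and "Re-instruction by the dental hygienist".

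Under Clinical parameters, "Both are assessed by two blinded and calibrated examiners at four sites per tooth". Under Statistical analysis, "On the site level, T-QHI is converted into a dichotomous index", and the odds ratio and confidence interval for a plaque-free site "are calculated with logistic regression analysis with a significance level of" 0.05. No period, sequence or patient term is mentioned. The section excludes none of these; it is silent.

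**The concern.** In a two-period crossover, a difference between periods cancels from the treatment contrast only if the two sequences are equal in size or if period is in the model. This plan secures neither. A period difference is plausible: by the second period a patient has had 30 days of practice and a second instruction session. If more patients start on the cylindric brush, the waist-shaped brush is used more often in the better-practised period and gains credit for it. If more start on the waist-shaped brush, it is penalised. The reported odds ratio would then partly reflect the fall of the coin. With no prespecified model, period could also be added or left out after the split and the data are known.

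**Working it through.** **Inputs from the protocol.** 20 patients; two sequences; coin toss; more than 23 natural teeth, so at least 24; four sites per tooth. The plan gives no figure for a period effect, between-patient variation or a target split, so there is nothing of its own to reproduce here. The basis for 20 patients is a cited study without an effect size, and it is not disputed on this point.

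**Assumptions.** A fair coin tossed once per patient; 24 × 4 = 96 sites per patient; 50% of sites plaque-free at baseline; on the logit scale, a patient SD of 0.7 and a patient-by-period SD of 0.4; period odds ratios of 1.25, 1.5 and 2.0, where above 1 means cleaner in period 2.

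**1. How uneven is the split?** Binomial(20, 0.5):
- exactly 10/10: 0.176, so uneven with probability 0.824
- 8/12 or closer: 0.737
- 7/13 or worse: 0.263
- 6/14 or worse: 0.115
- mean of |n2 − n1|/20: 0.176

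**2. How much period effect enters?** Let n1 patients be waist-shaped first and n2 cylindric first. The waist-shaped brush is used in period 2 by n2 of 20 patients and the cylindric brush by n1 of 20. Without a period term, the brush log odds ratio therefore shifts by about (n2 − n1)/20 × ln(period OR). The share is 0 at 10/10, 0.2 at 8/12, 0.3 at 7/13 and 0.4 at 6/14.

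A pooled site-level model ignores patient differences, so it sees a marginal period odds ratio of 1.22, 1.43 or 1.84 in place of 1.25, 1.5 or 2.0. At 6/14 with period OR 1.5, exp(0.4 × ln 1.43) ≈ 1.15. By numerical integration, the apparent odds ratio for a brush with no effect is:

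| Period OR | 8/12 | 7/13 | 6/14 | 12/8 | 13/7 | 14/6 |
|---|---|---|---|---|---|---|
| 1.25 | 1.04 | 1.06 | 1.08 | 0.96 | 0.94 | 0.92 |
| 1.5 | 1.07 | 1.11 | 1.15 | 0.93 | 0.90 | 0.87 |
| 2.0 | 1.13 | 1.20 | 1.27 | 0.89 | 0.83 | 0.79 |

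(Columns are n1/n2.) At period OR 1.1 the value is at most 1.03, even at 6/14. A 30% baseline changes the period OR 1.5 row by no more than 0.002.

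**3. Type I error of the plain site-level model (simulation).** At period OR 1.5 it is 32% at 10/10, 39% at 8/12, 47% at 7/13 and 57% at 6/14. Averaged over tosses it is 32% with no period effect and 35%, 40% and 49% at period OR 1.25, 1.5 and 2.0. The 32% comes from clustering alone; adding period but not patient only returns the error to about that level. The increment depends on the patient-by-period SD: at period OR 1.5, the average goes from 13% to 28% at SD 0.2, and from 47% to 50% at SD 0.6.

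**4. With clustering handled: patient-level test.** Each patient's log-odds difference is the brush effect ± ln(period OR) plus normal error with SD 0.7; the true brush OR is 1.6. A paired t-test without period (19 df) is compared with the two-period crossover estimator (18 df).
- Average power without period: 81%, 78%, 69% and 52% at period OR 1.0, 1.25, 1.5 and 2.0. With period it is 79% throughout.
- At period OR 1.5, power without / with period: 71% / 81% at 10/10, 91% / 77% at 7/13, 45% / 77% at 13/7.
- Type I error without period at period OR 1.5: about 5% averaged over tosses, but about 2% at 10/10 and 11% at 6/14. With period it stays near 5% at each split.

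**5. Break-even.** Without period, the mean squared error over tosses is 0.7²/20 + [ln(period OR)]²/20, because the mean of ((n2 − n1)/20)² is 1/20. The root is 0.156 at period OR 1.0, 0.162 at 1.2 and 0.181 at 1.5. With period it is 0.161 throughout. The period term starts to pay at a period OR of about 1.2.

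**The case against.** The harm needs both an uneven split and a period effect, and the protocol documents neither. It also limits the second: cleaning and instruction precede both periods, so period ORs of 1.5 or 2.0 have no support in the text. About 74% of tosses give 8/12 or closer, where the shift is at most 1.04 at period OR 1.25. The estimate is unbiased over repeated tosses. Most of the average power loss is not caused by the coin: at period OR 1.5, power without the period term is already 71% at an exact 10/10 split, against 69% averaged over tosses. The high type I error rates belong mainly to clustering. The 96 sites per patient are also assumed, since teeth with ceramic restorations and implants are left out of the analysis.

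All of this stands as a limit on size. It does not remove the point. The trial will have one split, and the odds ratio and error rate are conditional on it. Handling clustering alone leaves that shift in place. That power is lost even at 10/10 argues for the period term, because blocking alone would not recover it. Silence in so short an analysis section does not rule out a period term, but it commits nobody to one.

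**Conclusion.** The concern holds, as a worthwhile and cheap improvement, not a fatal flaw. As written, the plan gives unequal sequences with probability 82% and passes (n2 − n1)/20 of any period log odds ratio to the brush estimate, in either direction. The mean absolute shift over tosses corresponds to an odds ratio of 1.03, 1.06 or 1.11 at a period OR of 1.25, 1.5 or 2.0. It becomes material with a large imbalance or a large period effect, and is negligible below a period OR of about 1.2. The split probabilities require only a fair coin; every other size rests on assumed period effects, variances and site counts. Confidence is medium because the period effect is undocumented and the missing period term is inferred from silence.

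**What to change.** **Analysis.** Prespecify period as a fixed effect in a model that accounts for patient. Either of these would do:
- the two-period crossover estimator on patient-level summaries, that is, the mean of the two sequence-specific average differences. On patient empirical logits from the site-level simulation its type I error was 4.7% to 5.3% across splits from 6/14 to 14/6;
- a mixed logistic model, or a GEE logistic model with a small-sample correction, with patient as the cluster. With 20 clusters the correction matters. At period OR 1.5, a robust test with only the n/(n − 1) factor and a normal critical value gave 6.8% at 10/10 and 8.7% at 6/14; the Mancl–DeRouen variance with t(17) gave about 4%.

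A period term added to the plain site-level regression is not enough.

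**Allocation.** For patients not yet allocated, replace the coin with a concealed, pre-generated blocked list aimed at 10 per sequence. Recruitment opened on 1 September 2017, before the protocol date of 10 October 2017, so this may not reach everyone. The period term works whatever the split.

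**Cost.** One degree of freedom and a list; no extra patients or visits. The period term multiplies the variance by 100/(n1 × n2): 100/96 = 1.04 at 8/12, 100/91 = 1.10 at 7/13 and 100/84 = 1.19 at 6/14, or about 6% averaged over tosses. If there is truly no period effect, average power falls from 81% to 79%; at 10/10 it stays at 81%.

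### The one-week wash-out has no place in the visit schedule, which may make plaque scoring later after cleaning in period 2, and the logistic model names no period term

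*Combined protocol and SAP*

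**What the plan says.** The Study design section gives the layout as "Crossover: Two intervention periods of 30 days each; wash out period one week" and the allocation as "Randomized-controlled by toss of a coin". No balancing of the two sequences is described.

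The schedule under Clinical intervention runs as follows:

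- Visit 1 has "Pre-intervention: professional tooth cleaning", then instruction in both brush types, then randomization. The first 30-day period follows.
- Visit 2 has outcome scoring, then cleaning, then "Re-instruction by the dental hygienist".
- The next entry is "Second intervention period 30 days: Group 2 using waist-shaped and group 1 using cylindric brushes".
- Visit 3 has outcome scoring, then cleaning.

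The wash-out does not appear in this list. Toothbrush and toothpaste are fixed, and participants are "instructed not to use any chemical oral rinsing solution during the study period". Nothing says how interdental spaces are cleaned during the wash-out week.

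Under Statistical analysis, plaque is made dichotomous at site level and "the odds ratio and confidence interval (CI) for establishing plaque free interdental sites are calculated with logistic regression analysis". No period or sequence term is mentioned.

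**The concern.** Plaque is the primary outcome, and professional cleaning resets it. In a crossover, the time from that reset to scoring is therefore a natural thing to hold equal between periods. If the wash-out week sits after the Visit 2 cleaning, the second score is taken a week later after cleaning than the first, and that week has no defined interdental cleaning. If plaque depends on that interval, the periods differ for a reason unrelated to the brush.

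A period difference does no harm to the brush comparison when the sequences are equal in size or when the model adjusts for period. The plan secures neither. The stake is thus a chance shift in the brush odds ratio, which would depend on how the coin tosses fall.

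**Working it through.** The plan states no interval from cleaning to scoring, so there is no figure to reproduce.

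**Step 1: where the week could go.** The inputs are two 30-day periods and a 7-day wash-out (Study design) and the visit order (Clinical intervention). Period 1 is taken to start at Visit 1.

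| Placement of the week | Cleaning to scoring, period 1 / period 2 (days) | Conflict with the text |
|---|---|---|
| After the Visit 2 cleaning and re-instruction | 30 / 7 + 30 = 37 | None |
| Before the Visit 2 scoring | 30 + 7 = 37 / 30 | Scoring comes a week after the assigned brush was stopped |
| Between Visit 2 scoring and Visit 2 cleaning | 30 / 30 | Visit 2 is listed as a single visit |
| No actual gap | 30 / 30 | A one-week wash-out is specified |

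Only the first row keeps the wash-out, a single Visit 2, and scoring at the end of each 30-day period. The period 2 interval is then 37/30 = 1.23 times that of period 1. Brush use is 30 days in both periods.

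**Step 2: how a period effect reaches the brush comparison.** Let n1 be the size of group 1 (waist-shaped first), n2 the size of group 2 (cylindric first), n1 + n2 = 20, and d the period log odds ratio (period 2 against period 1). Assume equal numbers of sites per participant. Waist-shaped data come from period 2 for a share n2/20 of participants, and cylindric data for a share n1/20. Without a period term, the brush log odds ratio shifts by

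d × (n2 − n1)/20.

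**Step 3: how unequal the sequences may be.** With Binomial(20, 0.5):

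- P(10:10) = 184,756/1,048,576 = 0.176
- P(13:7 or worse) = 0.263
- mean of (n2 − n1)/20 = 0
- mean of |n2 − n1|/20 = 0.176

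**Step 4: illustrative size.** The documents give no period effect, so the period odds ratios of 1.1 and 1.2 are assumptions. The spurious brush odds ratio is the period odds ratio raised to the power (n2 − n1)/20.

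| Sequence split (n1:n2) | Period OR 1.1 | Period OR 1.2 |
|---|---|---|
| 10:10 | 1.00 | 1.00 |
| Average imbalance (power 0.176) | 1.02 | 1.03 |
| 7:13 (power 0.3) | 1.03 | 1.06 |

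If the period effect or the imbalance runs the other way, the reciprocals apply.

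**Step 5: check of the formula and the remedy.** I fitted logistic regressions to expected counts at 7:13, with no true brush effect, equal sites per participant and assumed period 1 plaque-free proportions of 0.2, 0.4 and 0.6. The unadjusted brush odds ratios were 1.029 (period OR 1.1) and 1.056 (period OR 1.2) at every proportion. With a period term, all were 1.000.

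**The case against.** The strongest reply is that the 37 days are inferred. The schedule gives no visit days. If the team in practice splits Visit 2 around the week, or runs no gap, the intervals are equal. This stands: what is certain is that the week is unplaced, and 30 versus 37 is only the reading that fits the text best.

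The second reply is that 23% more time is not an effect size. The same 30 days of assigned brush use come directly before each scoring, and nothing in the documents shows that plaque depends on a week's difference in the earlier cleaning. This also stands, and it is why the effect is probably small.

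The third reply is that the odds ratios above come from assumed period effects, the coin toss and the missing period term, and would apply to any period effect. That is correct. The wash-out placement adds one avoidable source, and its own contribution is not quantified. Site numbers also differ between participants, because tooth counts vary and some teeth are excluded, so the formula is approximate.

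A reader might infer three stronger things that the documents do not support:

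- **Bias towards one brush.** Each brush is used in period 2 by one of the groups, and the expected shift in the log odds ratio over coin tosses is zero.
- **Plaque carry-over.** The Visit 2 cleaning already removes plaque between periods.
- **A handicap from the delay between re-instruction and use of the second brush.** Both brushes are taught at Visit 1, and Visit 2 adds a further instruction on every reading.

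**Conclusion.** The point holds as a minor one. The wash-out is specified but unplaced, and interdental cleaning during it is undefined. On the best-fitting reading, plaque is scored 30 days after cleaning in period 1 and 37 days after it in period 2. Any resulting period effect is shared by both brushes. It matters only because unrestricted coin tossing leaves the sequences unequal in 82.4% of cases (100 − 17.6) and the model names no period term.

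The conclusion rests on period 1 starting at Visit 1, on all Visit 2 items falling on one day with the week after them, and, for the shift formula, on equal sites per participant. The odds ratio shifts are illustrations, not estimates.

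**What to change.** **Add period as a term in the site-level logistic model.** This is one extra term, costs essentially nothing, and protects against any period effect that is common to both sequences, whatever its source.

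**Place the wash-out between Visit 2 scoring and the already planned cleaning and re-instruction.** Score on day 30, clean and re-instruct on day 37, and score again on day 67. Cleaning to scoring is then 30 days in both periods. The cost is one extra attendance per participant, 20 in all. Total duration is 30 + 7 + 30 = 67 days, the same as on the best-fitting reading of the present plan. The plan's dates ("Data collection period: December 1", taken as 2017, to 30 March 2018) span 119 days, so this fits if Visit 1 takes place by 22 January 2018.

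**State which interdental cleaning participants use during that week.** This takes one sentence.

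Deleting the wash-out and relying on the Visit 2 cleaning would also equalise the intervals. I would not recommend it on this evidence: papillary bleeding is the secondary outcome, and the documents do not show that cleaning alone resets it.
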